## 1. BACKGROUND, OBJECTIVES, & STUDY DESIGN

Ankle syndesmosis disruption due to ankle trauma is associated with significant pain and disability.  Surgical stabilization procedures typically involve an internal fixation of the distal tibiofibular joint to restore the spatial relationship of the bony structures. Rigid fixation has traditionally been the technique of choice for stabilizing the syndesmosis; however, dynamic fixation options like the TightRope® system (Arthrex®, Naples, United States) have more recently demonstrated some advantage over rigid screw fixation techniques as they attempt to mimic the dynamic nature of the syndesmosis.  Tightrope or flexible fixation is still a non-anatomic reduction and stabilization technique and as such is only an approximation of the syndesmotic ligaments.

Anterior inferior tibiofibular ligament (AITFL) augmentation techniques using nonabsorbable suture materials (*Internal*Brace, Arthrex®, Naples, United States) have been used to supplement syndesmotic fixation in order to more accurately reconstruct the syndesmosis and restore native biomechanics.  Clinical research assessing the use of the *Internal*Brace as an additional stabilization method is lacking and the minimum required stability to achieve successful clinical and patient-reported outcomes remains unclear.

The primary objective of this study is to evaluate the quality of syndesmotic reduction as determined by weight bearing 3-D relative volumetric ratio between ankles in patients undergoing syndesmotic stabilization with and without an *Internal*Brace augmented repair of the AITFL to determine if the technique influences the reduction and postoperative stability of the syndesmosis. This will be compared at both 6-weeks and 3-months post-operation. Our

secondary objectives are 1) to determine whether the addition of the *Internal*Brace augmentation to the traditional TightRope fixation procedure improves short- and long-term patient-reported ankle function and generic health ratings and 2) to explore relationships between syndesmotic volume and patient-reported outcomes across groups.

#### **Design**

We will use a prospective, two-arm, single-blind, randomized study design to conduct our pilot study. After informed consent, twenty patients will be randomized evenly into a traditional TightRope fixation group or a TightRope fixation with an AITFL augmentation group upon enrollment into the study. As this is a pilot study with a small sample size, block randomization will be used to reduce the risk of unequal group sizes between groups. A researcher who will not otherwise be involved in patient interactions will serve as the randomization coordinator for this trial. They will prepare a randomization schedule using the freely accessible tools available at www.randomization.com. The sequence generator uses block randomization procedures based on the number of interventions and patients needed in each block and creates a schedule based on the patient ID number. Due to the potential emergent nature of injuries involved in this study and a short time between enrollment and surgery, the surgeon may need to acquire the group allocation shortly after enrolling patients to be able to prepare for the surgery and so the schedule will be converted to a Google Document that can then be accessed by the surgeon/PI to reveal the intervention allocation. Since pre-operative and post-operative instructions are the same regardless of the procedure, the participants will be blinded to their intervention group until the completion of the study period.

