#### **Participant Population**

Due to the nature of the study population needed, potential participants will be recruited from the clinic or corresponding hospital of the study doctor. Patients will be considered for inclusion in the study if they are over 18 years old and demonstrate unilateral ankle trauma causing syndesmotic disruption (e.g., ligamentous rupture, and/or bimalleolar and trimalleolar ankle fractures) and are determined to be good candidates for TightRope fixation surgery outside of the research context. Exclusion criteria is as follows: Illiterate patients, non-English speakers, minors, patients with diminished mental capacity, or any patient needing a legally authorized representative, pregnant patients, patients that have had a previous ankle surgery, have an open fracture, fractures that require posterolateral approach, or any contralateral foot or ankle injury. I Additionally, patients will also be excluded if they are unable to complete the CT scans necessary for completing the volumetric assessments, or if upon surgical exposure, the AITFL remains intact. In the case of the latter, the patients would still receive appropriate procedures necessary for treating their ankle trauma but would be excluded from the study.

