#### Participant Enrollment and/or Screening

Patients will be identified in the clinic or hospital by the study doctor. Patients will be consented for syndesmotic open reduction surgery using the TightRope system which will indicate the patient for potential inclusion into the study. Patients will then be screened for exclusion criteria listed above and if no exclusion criteria are present, the patient would be considered for inclusion and the informed consent process would begin.

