#### 2. STUDY PROCEDURES

Prospective patients will enter the clinic or hospital associated with the study doctor seeking care after ankle trauma. Patient will be moved through clinic/hospital workflow as normal. Once the patient elects to undergo syndesmotic stabilization surgery and is over 18 years of age, study protocol will be triggered as follows:

1. The study doctor will do an initial clinical screening for open fractures or fractures that would require a posterolateral approach during his examination, and if present, the patient will be excluded. If patients are not excluded at this point, the study doctor or another

member of the research team will enter the room and work through the informed consent process with the goal of obtaining the consent. Patient will have ample opportunity to read through documents to their desire. Patient will be asked if they are literate and speak English comfortably and excluded if they do not answer yes to both questions.

- 2. Once the consent is signed, a research team member will review patient's medical history for presence of other exclusion factors: previous ankle surgery, or any contralateral foot or ankle injury. If any exclusion factor is present, consent documents will be shredded.
- 3. If no exclusion factors are present at this point, the following will occur:
  - a. The patient will be issued a participant ID number and will complete the preoperative patient-reported outcomes (PROs) related to their perceived ankle function (The Foot and Ankle Outcome Score) and generic health status (SF-36). These will be administered by a research team member by using either paper format, or a tablet computer through a survey administration software called Surgical Outcome System (SOS).
  - b. The participant ID will be used by the study doctor to verify their randomized group allocation schedule generated by block randomization procedures described above and will be scheduled for their respective surgery.
- 4. Patient will follow typical pre-operative procedures. During the procedure, the patients will be in a supine position so that the fibula and the lateral ankle ligaments can be exposed. The integrity of the AITFL will be examined by the study doctor, and if disrupted the participant will be included in the study and will undergo either the traditional TightRope fixation procedure or the double stabilization procedure (TightRope fixation plus *Internal*Brace augmentation) as assigned and performed by the

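### The surgeon can open the whole allocation schedule and knows the arm when judging AITFL eligibility at surgery, and no record by arm of patients excluded there is planned

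*Combined protocol and SAP*

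**What the plan says.** **Who holds the list.** Under Design, "A researcher who will not otherwise be involved in patient interactions will serve as the randomization coordinator for this trial", and that person prepares a block schedule keyed to patient ID. The block size is not given. The same section then says that "the schedule will be converted to a Google Document that can then be accessed by the surgeon/PI to reveal the intervention allocation". It gives a reason: injuries may be emergent and the interval before the operation brief, which is why "the surgeon may need to acquire the group allocation shortly after enrolling patients to be able to prepare for the surgery". It describes no release of one assignment at a time, no masking of later rows and no access record.

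**Who enrols.** Participant Enrollment and/or Screening states: "Patients will be identified in the clinic or hospital by the study doctor". In Study Procedures step 1, "The study doctor will do an initial clinical screening for open fractures" and for fractures needing a posterolateral approach. Consent Process and Documentation lets the study doctor or another team member take consent. The history check in step 2 lies with someone else: "Once the consent is signed, a research team member will review" the medical history.

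**Order of events.** Randomisation of twenty patients, split evenly, takes place at enrolment. At step 3b the study doctor uses the participant ID to find the arm and the patient is scheduled accordingly. At step 4 the study doctor inspects the AITFL, and inclusion depends on the finding. The two procedures are described separately only in steps 5 and 6.

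**The exclusion and its record.** Participant Population excludes a patient "or if upon surgical exposure, the AITFL remains intact". Step 4 includes if the ligament is disrupted and excludes if disruption is not confirmed. For a patient excluded at that point, the study documents are shredded. Step 7 enters pre-operative data for eligible participants only.

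**The concern.** Randomisation protects a comparison only if whoever decides on entry does not know the coming assignment, and if patients are not removed after assignment by someone who knows it. The plan leaves both open. A surgeon who can read later rows could, knowingly or not, time or steer enrolment. A surgeon who knows the arm could resolve an uncertain AITFL finding differently in the two arms. With about 10 patients per arm, one or two such decisions form a visible share of the data.

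The third element is accountability. For patients randomised and then excluded at surgery, shredding removes the documented reason and the pre-operative data, and no report of numbers by arm is planned. A reader of the results could not easily tell whether these exclusions were balanced.

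Blinding of participants and of the volume readers (Primary Outcomes) protects response and measurement. It does not protect who enters or stays in the trial.

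**Working it through.** The plan gives no figure on this point, so there is nothing to reproduce. The check has a procedural part and an illustration of scale.

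**1. Sequence.**

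| Step | Act | By whom | Arm known? |
|---|---|---|---|
| Enrollment section, step 1 | Identify patient, first screen | Study doctor | Could be, if later rows are visible |
| Consent section | Consent | Study doctor or team member | As above |
| Step 2 | History review | Team member | Not stated |
| Step 3b | Look up arm | Study doctor | Yes, from here |
| Step 4 | Judge AITFL, include or exclude | Study doctor | Yes |
| Step 4, end | Shred documents if excluded | Not stated | – |

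That the surgeon/PI of the Design section is the study doctor of Study Procedures is an inference. Steps 3b and 4 alone, however, give the study doctor both the look-up and the AITFL judgement.

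**2. Predictability of the next assignment.** With the open schedule it is 100%. With release one at a time, the best guess is the arm used less often so far in the block (ties count 0.5). Averaged over all balanced sequences, this is right 75%, 71%, 65% or 62% of the time for assumed blocks of 2, 4, 10 or 20. If the block size is known, 50%, 33%, 17% or 9% of assignments are certain. One-at-a-time release therefore reduces foreknowledge but does not abolish it, and the block size should stay undisclosed.

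**3. Bias from selective exclusion (all rates assumed).** Let latent severity be N(0,1) and let the least severe share q be excluded. The mean of those kept is φ(z_q)/(1−q):

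- q = 0.10: 0.1755/0.90 = 0.195
- q = 0.20: 0.2800/0.80 = 0.350
- q = 0.30: 0.3477/0.70 = 0.497

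The difference between arms is 0.155 SD for 10% v 20% and 0.302 SD for 10% v 30%. Multiplying by an assumed severity–outcome correlation of 0.3 or 0.5 gives the outcome shift:

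- 10% v 20%: 0.046 or 0.077 SD
- 10% v 30%: 0.091 or 0.151 SD

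For comparison, chance imbalance with 10 per arm has SD √(2/10) = 0.447.

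**4. Type I error.** The SAP uses t-tests at 0.05 (two-sided assumed, as sidedness is not stated). The noncentrality is shift/[s_p√(1/n₁+1/n₂)], with s_p the pooled SD after truncation.

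| Exclusion | n | Correlation | Noncentrality | Type I error |
|---|---|---|---|---|
| 10% v 20% | 9 v 8 | 0.3 | 0.097 | 5.1% |
| 10% v 20% | 9 v 8 | 0.5 | 0.167 | 5.3% |
| 10% v 30% | 9 v 7 | 0.3 | 0.183 | 5.3% |
| 10% v 30% | 9 v 7 | 0.5 | 0.315 | 6.0% |

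An extreme case is exclusion, in one arm only, of exactly the patients with the worst outcomes, with 10 randomised per arm and no replacement. By simulation (100,000 runs), one such exclusion gives 0.17 SD and 7.5%, two give 0.32 SD and 11.6%, and three give 0.46 SD and 16.9%. This is an upper bound, because no surgeon can know the outcomes in advance. Exclusions unrelated to arm and outcome add no bias.

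**5. What a log could detect.** A two-sided Fisher test on 10 v 10 randomised has power 1.2% for 10% v 20% and 5.7% for 10% v 30%. An observed 1/10 v 3/10 gives p = 0.58. A log makes exclusions visible but cannot show that they were balanced, so limiting access to the schedule comes first.

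**The case against.** The strongest reply is operational. Injuries may be emergent, and the surgeon may need the arm in advance to prepare. This stands as a reason to see one patient's arm early. It does not call for access to the whole schedule, but it does argue against making release in theatre the required fix.

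The look-up is described as following enrolment, by an ID issued after consent and history review. A reader might infer that the surgeon will see or use later assignments. The documents do not say so; they only state no limit. Nor does the study doctor control all screening, since step 2 belongs to another team member.

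The AITFL criterion is prespecified and the same in both arms. That stands too. What remains open is how a partial or uncertain tear is classed, and nothing shows that such cases are common.

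A reader might also infer that shredding makes exclusions by arm impossible to reconstruct. That goes too far. The schedule is keyed to patient ID and is not said to be destroyed, so if IDs are issued in order and not reused, IDs missing from the spreadsheet could give a partial count. The surgical record is not said to be destroyed either. Nor does this shredding hide selective enrolment: it concerns only patients already allocated and exposed at surgery, whereas selective enrolment acts before that.

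Finally, this is a 20-patient pilot with blinded volume readers, and the illustrated bias is well below chance imbalance. This lowers the rating but does not remove the point, because the SAP still tests between-group differences at 0.05.

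**Conclusion.** The point holds and should be fixed. Three stated procedures weaken concealment and accountability: open access to the schedule with no stated per-patient limit, an eligibility decision after randomisation by someone who knows the arm, and shredding of the study documents of those excluded, with no planned count by arm. Misuse is permitted, not shown.

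The likely effect is small and its direction unknown. The range of 0.05 to 0.15 SD, with type I error of 5.1% to 6.0%, rests on assumed exclusion rates of 10% v 20% or 30% and assumed correlations of 0.3 to 0.5; the documents give neither. These figures do not support calling the trial's comparison invalid. The case for change rests on how cheaply the gap can be closed.

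**What to change.** 1. **Release of assignments (Design and step 3b).** The existing randomisation coordinator holds the schedule, does not disclose the block size, and releases one assignment at a time after that patient's enrolment is logged. The early look-up that the Design section needs is kept.
2. **Record of exclusions (step 4 and Consent Process and Documentation).** Replace shredding with a de-identified log of every intra-operative exclusion: ID, arm, recorded AITFL finding and reason. Report exclusions by arm. Adapt the consent wording, which tells patients that data are destroyed as early as possible.
3. **Wording.** Reconcile the AITFL exclusion wording in Participant Population with the two statements in step 4, so that the classing of a partial or uncertain tear is documented.

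**Option, not default.** Where the site finds it feasible, release the assignment only after the AITFL finding is recorded. This alone conceals the arm at that decision. Its price is that materials for both procedures must be available for each case and that surgery can no longer be scheduled by arm. Without this option the arm stays known at the AITFL decision, and the report should say so.

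**Cost.** Items 1 to 3 need a protocol and consent amendment, the existing coordinator's time and a log. They add no patients to the analysed sample.

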#### **Participant Population**

Due to the nature of the study population needed, potential participants will be recruited from the clinic or corresponding hospital of the study doctor. Patients will be considered for inclusion in the study if they are over 18 years old and demonstrate unilateral ankle trauma causing syndesmotic disruption (e.g., ligamentous rupture, and/or bimalleolar and trimalleolar ankle fractures) and are determined to be good candidates for TightRope fixation surgery outside of the research context. Exclusion criteria is as follows: Illiterate patients, non-English speakers, minors, patients with diminished mental capacity, or any patient needing a legally authorized representative, pregnant patients, patients that have had a previous ankle surgery, have an open fracture, fractures that require posterolateral approach, or any contralateral foot or ankle injury. I Additionally, patients will also be excluded if they are unable to complete the CT scans necessary for completing the volumetric assessments, or if upon surgical exposure, the AITFL remains intact. In the case of the latter, the patients would still receive appropriate procedures necessary for treating their ankle trauma but would be excluded from the study.

#### Participant Enrollment and/or Screening

Patients will be identified in the clinic or hospital by the study doctor. Patients will be consented for syndesmotic open reduction surgery using the TightRope system which will indicate the patient for potential inclusion into the study. Patients will then be screened for exclusion criteria listed above and if no exclusion criteria are present, the patient would be considered for inclusion and the informed consent process would begin.

#### Withdrawal of Subjects

Participants will be withdrawn from the study if any of the following conditions exist:

- 1. Participant voluntarily withdraws from the study
- 2. Participant death

- 3. Participant who, in the opinion of the PI, would be compromised by continued study participation
- 4. Participant experiences an AE that, in the opinion of the PI, necessitates removal from the study, including unresolved SAE or death
- 5. Participant experiences an intercurrent illness, injury, or other reason that would, in the opinion of the PI, affect the assessment of clinical outcomes or the conduct of the study to a significant degree
- 6. Participant fails to comply with protocol requirements
- 7. Administrative reasons (e.g., PI decides to discontinue the study)

Under these conditions, all patient data will be immediately destroyed. During the consent process, participants will be informed of their right to withdraw from the study at any time for any reason and without prejudice to alternative treatment. For subjects lost to follow-up, the research team should attempt to contact the patient via phone a minimum of three times before considering them lost to follow-up. Participants who withdraw voluntarily or are discontinued by the PI will remain eligible for standard of care treatment by the PI and research team.

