## Adverse Events (AE) Definitions & Reporting

The research team will collect all adverse events (AE) during the study from the time of enrollment until the patient exits the study. The following definitions are intended to assist the research team in the identification of AEs. The research team will follow applicable regulatory requirements to report AEs to regulatory authorities and to the IRB.

Adverse Event (AE): An AE is any symptom, sign, illness or experience that develops or worsens in severity during the course of the study whether it is related or unrelated to the investigational device or its use. An AE need not be symptomatic to be reportable, e.g., device disruption detected on imaging that would require treatment, or psychological distress or discomfort associated with survey instruments.

Serious Adverse Event (SAE): An SAE is any AE that is:

- Fatal
- **Life threatening:** the participant is at risk of death (could have died without intervention) at the time of the event. This does not apply to any *hypothetical* risk of death if the AE were more severe or were to progress.
- Require or prolongs a hospital stay: Greater than 1 day (24 hours)

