## • Permanent impairment to a body structure or body function

Relationship of AE to the study: The relationship of the AE to the study devices or procedures will be classified as either:

- **Related**: The adverse event has a reasonable temporal relationship to the use of the device or the procedure and cannot reasonably be explained by known characteristics of the participant's clinical state or other therapies.
- Not Related: The adverse event is due to the underlying disease state or is due to concomitant medication or therapy not related to the use of the device.
- **Unknown**: If the adverse event cannot be determined to have a causal relationship, it will be classified as unknown.

Unanticipated: The sponsor is responsible for classifying AEs as anticipated or unanticipated according to the accepted regulatory definitions.

The PI and research team will be responsible for ensuring participants' safety daily and for the reporting of any SAEs and unanticipated AEs that are determined relevant to the devices or study procedures. For reportable events, the research team will follow applicable regulatory requirements to report the event to regulatory authorities and to the IRB immediately.

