#### STUDY RISKS & BENEFITS

#### Potential Risks to Study Participants & Risk Mitigation

- 1. Potential Risk: Loss of confidentiality
  - Risk Mitigation: All reasonable barriers will be in place to protect against the potential loss of confidentiality:
    - Data will be de-identified and data collection tools used to collect participants data will use unique subject ID numbers for identification
    - ii. Only generic demographic variables (e.g., age, sex, race) needed to evaluate participant characteristics will be captured in data collection
    - iii. Study materials and data collection tools will be kept in secure, locked areas only accessible to research team
    - iv. Electronic spreadsheets will only be accessible to assigned authorized personnel and will be password protected
    - v. Imaging (e.g., CT scan) will only be accessible by PI and clinical staff, and will be de-identified and labeled with subject ID numbers before

- volumetric assessments are completed
- vi. Study records will be continually monitored by study coordinators to ensure all data is de-identified. Any oversights will be corrected and research team members will be notified.
- 2. Potential Risk: Harm from radiation exposure during weight-bearing CT scan
  - Risk Mitigation: All reasonable limitations and protections against potential
    adverse health effects that may be associated with radiation exposure will be in
    place:
    - Patients that are not able to complete the WBCT necessary for volumetric assessments will be excluded
    - ii. During the consent process, the research team and the participant will discuss and assess the participant's exposure history and determine if the potential risk is acceptable for that participant. The participant will be given the opportunity to decline to participate in the study and not undergo the WBCT without any loss of benefits to which the participant was otherwise entitled.
- 3. Potential Risk: Surgery and surgical device implantation risks including infection and foreign body reactions or sensitivities. Other specific adverse effects noted for the study devices include: osteomyelitis surrounding the TightRope, failure of the implant resulting in re-diastasis, and painful aseptic osteolysis related to the wear of the FiberWire (not noted for XP). The InternalBrace does not have any known increased risk beyond potential material sensitivity.
  - Risk Mitigation: All reasonable limitations and protections against potential

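### The PI may remove a participant for an unresolved SAE and AE collection ends at exit, so the plan has no study follow-up of that event after removal

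*Combined protocol and SAP*

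**What the plan says.** Four parts of the combined protocol and SAP bear on this.

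- **Withdrawal of Subjects (section 1).** The list opens in mandatory terms: "Participants will be withdrawn from the study if any of the following conditions exist". Condition 4 is "Participant experiences an AE that, in the opinion of the PI, necessitates removal from the study, including unresolved SAE or death". For those who leave, the section says: "Participants who withdraw voluntarily or are discontinued by the PI will remain eligible for standard of care treatment by the PI and research team".
- **Adverse Events (AE) Definitions & Reporting (section 3).** "The research team will collect all adverse events (AE) during the study from the time of enrollment until the patient exits the study". For reportable events the team is to "report the event to regulatory authorities and to the IRB immediately".
- **Study Procedures (section 2), item 9.** PROs are due at 6 weeks, 3 months, 6 months and 1 year. Bilateral WBCT is due at 6 weeks and 3 months.
- **Potential Risks, item 3.** The device risks named include bone infection around the TightRope, "failure of the implant resulting in re-diastasis", and painful osteolysis.

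The Design section lets the surgeon/PI look up the allocation, and under Study Procedures the study doctor performs the assigned operation.

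**The concern.** The treatment is one operation whose implants remain in place. Removing a participant from the study therefore does not end exposure to the device. It ends observation.

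Two things are at stake. The first is safety information. The background section says clinical research on the augmentation is lacking, so the course and outcome of serious events by arm are among the more useful things a 20-patient pilot can record. The withdrawal rule and the AE window together allow that record to stop while the event is still open.

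The second is missing outcome data. A participant removed for a serious complication also loses the remaining PRO and WBCT assessments. Those values could be missing because the result was poor, and the decision rests with someone who knows the arm. The Statistical Analysis Plan specifies separate t-tests at each time point and gives no method for missing data.

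**Working it through.** The plan states no figure on this point, so the check is mainly a reading of the sections against each other.

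**Step 1: Is an unresolved SAE a ground for removal?** Yes, within a PI judgment. Condition 4 turns on the PI's opinion that removal is needed, and it names an unresolved SAE as an included case. The SAE definition includes permanent impairment of a body structure or function. On an ordinary reading such an event does not resolve, so it falls within the named case.

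**Step 2: Does removal close AE collection?** Yes. Collection runs "from the time of enrollment until the patient exits the study", removal is an exit, and there is no extension for events still open.

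**Step 3: Does any other text restore follow-up?**

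| Place | What it provides | Restores study follow-up? |
|---|---|---|
| AE section, reporting paragraph | Immediate report of reportable events | No; no later outcome report is described |
| AE section, relationship to the study | Classification as related, not related or unknown | No; no later review is described |
| Potential Risks, item 3, mitigation iv | Reporting over the study timeline, referring back to the AE section | No; it inherits the same window |
| Withdrawal of Subjects, last sentence | Eligibility for standard of care | No; this is clinical care, not study data |
| Study Procedures, item 9 | Scheduled visits for participants | No; nothing for those removed |
| Statistical Analysis Plan | t-tests and correlations | No; silent on withdrawn patients |

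**Step 4: What is lost, by time of removal** (counted from the item 9 schedule)

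| Removal | PRO assessments lost | WBCT assessments lost |
|---|---|---|
| Before 6 weeks | 4 | 2 |
| 6 weeks to 3 months | 3 | 1 |
| 3 to 6 months | 2 | 0 |
| 6 months to 1 year | 1 | 0 |

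The primary volume ratio is affected only by removal before the 3-month scan. PROs are affected by removal at any time before 1 year.

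**Step 5: Weight of one removal.** Twenty patients split evenly give 20/2 = 10 per arm, so one removal is 1/10 = 10% of an arm. If the missing value would have lain k SD from the mean m of the other nine, the full arm mean would be (9m + m + k SD)/10 = m + k SD/10, a shift of k/10 SD. The documents give neither k nor a rate of such removals, so this formula shows sensitivity and does not estimate bias.

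**Step 6: Is this the same as the data-destruction order?** No. The withdrawal section also says "Under these conditions, all patient data will be immediately destroyed", which concerns data already held. If that sentence were deleted, prospective follow-up would still stop at exit.

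**The case against.** The strongest reply is that condition 4 is discretionary. A reader might infer that every unresolved SAE forces the participant out. The text does not support that, because the PI must first judge that removal is needed. This objection stands and limits the point to cases where the PI uses the ground. It does not remove the gap, since the rule names an unresolved SAE as a fitting case and the person judging knows the arm.

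A reader might also infer that patients with deep infection, implant failure or re-diastasis would all leave. That does not follow either. To be an SAE, an event must be fatal, be life-threatening, require or prolong a hospital stay of more than 24 hours, or cause permanent impairment. The AE section gives device disruption seen on imaging and needing treatment as an example of an AE, without calling it serious. Such patients could be removed; the documents do not say that they would be.

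The initial report of a reportable event is still required, causality is still classified, and removed patients may still be treated by the same team. All of that stands. What has no route is study collection of the event's later course and outcome, and of the remaining assessments.

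A third tempting inference is that the arm with more complications would look better. This is possible but not shown. A patient revised before the scan, or unable to bear weight for it, would not supply the failed value even if kept in the study.

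Finally, this overlaps with the destruction order. The two are logically distinct, but one rule on follow-up and retention after withdrawal could settle both, and they should not be counted as two unrelated defects.

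**Conclusion.** The point holds in limited form. When the PI uses condition 4 for an unresolved SAE, the plan as written stops study collection on that event and on the participant's remaining PRO and WBCT assessments, and no other section restores it. Safety data are then incomplete, and outcome data could be missing for a reason related to outcome.

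Each removal costs 10% of an arm. This assumes the planned 10 per arm and that removal counts as exit from the study. How many participants would be affected is unknown, and in a 20-patient pilot it may be none. The size and direction of any bias are likewise unknown. The plan should be changed because the remedy is cheap and condition 3 already lets the PI protect a participant who would be harmed by continuing, so dropping the named case removes no safeguard.

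**What to change.** 1. **Withdrawal of Subjects, condition 4.** Delete the words that name an unresolved SAE as an included case.
2. **Withdrawal of Subjects, conditions 3 to 5.** Reconcile these with the AE section. Conditions 3 and 5 give the PI similar discretion over the same patients, so changing condition 4 alone would leave the gap open. State that PI-directed discontinuation after surgery ends only those study procedures judged to compromise the participant, and that AE and PRO follow-up continue to 1 year unless the participant withdraws consent.
3. **AE section.** Replace study exit as the end of the collection window with 1 year after surgery, or with resolution or stabilisation of any AE still open if that is later, unless consent for follow-up is withdrawn.
4. **WBCT.** Set no new rule. Whether a participant with an ongoing complication has a scheduled scan stays a clinical judgment under condition 3.
5. **Consistency.** In the same amendment, make sure the destruction sentence does not apply to follow-up data kept under items 2 and 3.

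The cost is protocol wording, an IRB amendment and a few extra contacts for participants with an open AE. No new study procedure is needed.
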